24 YR. OLD HUMAN CORNEA¹

25 YR. OLD HUMAN CRYSTALLINE LENS²

*The data was obtained from measurements taken through the central 3.5 mm portion for the thinnest lens (-1.00D lens, 0.070 mm center thickness).

¹ Lerman, S., Radiant Energy and the Eye, MacMillan, New York, 1980, p.58, figure 2-21

² Wexler, M., Hinrichs, V.M., Optical Radiation and Visual Health, CRC Press, Boca Raton, Florida, 1996, p.19, figure 5

WARNING: UV absorbing contact lenses are NOT substitutes for protective UV absorbing eyewear, such as UV absorbing goggles or sunglasses because they do not completely cover the eye and surrounding area. The patient should continue to use UV absorbing eyewear as directed.

ACTIONS

In its hydrated state, the contact lens, when placed on the cornea, acts as a refracting medium to focus light rays on the retina. When hydrated and placed on the cornea for therapeutic use, the contact lens acts as a bandage to protect the cornea.

**Clinical Study Protocol
Johnson & Johnson Vision Care, Inc.**

APPENDIX D: BINOCULAR OVER REFRACTION

**Clinical Study Protocol
Johnson & Johnson Vision Care, Inc.**

APPENDIX E: PRESBYOPIA SYMPTOMS QUESTIONNAIRE

[REDACTED]

[REDACTED]

[REDACTED]

[figure not shown]
[REDACTED]

[REDACTED]

[REDACTED]

[figure not shown]
**Clinical Study Protocol
Johnson & Johnson Vision Care, Inc.**

APPENDIX F: OCULAR DOMINANCE

[figure not shown]

**Clinical Study Protocol
Johnson & Johnson Vision Care, Inc.**

APPENDIX G: LENS FITTING GUIDE

**Clinical Study Protocol
Johnson & Johnson Vision Care, Inc.**

Clinical Study Protocol
Johnson & Johnson Vision Care, Inc.

APPENDIX H: [REDACTED]

- [REDACTED] DETERMINATION OF NEAR ADD
- [REDACTED] NEAR logMAR VISUAL ACUITY MEASUREMENT PROCEDURE
- [REDACTED] LENS FITTING CHARACTERISTICS
- [REDACTED] SUBJECT REPORTED OCULAR SYMPTOMS
- [REDACTED] FRONT AND BACK SURFACE LENS DEPOSIT GRADING PROCEDURE
- [REDACTED] DETERMINATION OF DISTANCE SPHEROCYLINDRICAL REFRACTIONS
- [REDACTED] BIOMICROSCOPY SCALE
- [REDACTED] KERATOMETRY
- [REDACTED] DISTANCE AND NEAR VISUAL ACUITY EVALUATION
- [REDACTED] ETDRS DISTANCE VISUAL ACUITY MEASURMENT PROCEDURE
- [REDACTED] WHITE LIGHT LENS SURFACE WETTABILITY
- [REDACTED] VISUAL ACUITY CHART LUMINANCE AND ROOM ILLUMINATION
- TESTING

**Clinical Study Protocol
Johnson & Johnson Vision Care, Inc.**

DETERMINATION OF NEAR ADD

[figure not shown]
Title: **Determination of Near Addition**

Document Type: **Work Instructions**

[REDACTED]

Title: **Determination of Near Addition**

Document Type: **Work Instructions**

[REDACTED]

	If...	

A 2D binary image (black and white) showing a complex pattern. The pattern features several horizontal bands of black pixels, with some vertical and diagonal features. The image is framed by a thick black border.

6	
If the tentative ADD is too strong (too much plus), ask the patient to place the near point card at the desired test distance. Place -0.25D in front of both eyes (using +/- 0.25D flippers or loose trial lenses) and ask him/her to compare the tentative ADD with and without the -0.25D. If adding -0.25D does not reduce clarity add the -0.25D to the tentative ADD and repeat the procedure. Continue to add -0.25D until the patient begins to have a reduction in clarity.
 
With the additional power in place, measure the range of clear focus (i.e., clear focus zone).
 
  
 If the desired test distance is...	Then	
   
 Approximately midway within the clear focus zone	No further adjustments are necessary.	
 
 Near the edge of the clear focus zone closest to the patient	Add -0.25D and measure the range of clear focus again.	
 
 Near the edge of the clear focus zone furthest from the patient	Add +0.25D and measure the range of clear focus again.	
  
 
Repeat this step until the near point is approximately midway in the clear zone.
	If the desired test distance is...	Then	Approximately midway within the clear focus zone	No further adjustments are necessary.	Near the edge of the clear focus zone closest to the patient	Add -0.25D and measure the range of clear focus again.	Near the edge of the clear focus zone furthest from the patient	Add +0.25D and measure the range of clear focus again.
If the desired test distance is...	Then								
Approximately midway within the clear focus zone	No further adjustments are necessary.								
Near the edge of the clear focus zone closest to the patient	Add -0.25D and measure the range of clear focus again.								
Near the edge of the clear focus zone furthest from the patient	Add +0.25D and measure the range of clear focus again.								
7	
If the tentative ADD is too weak (too much minus), ask the patient to place the near point card at the desired test distance. Place +0.25D in front of both eyes (using +/- 0.25D flippers or loose trial lenses) and ask him/her to compare the tentative ADD with and without the +0.25D. If adding +0.25D improves clarity (visual acuity), add the +0.25D to the tentative ADD and repeat the procedure. Continue to add +0.25D until no more improvement in near visual acuity is achieved at the desired test distance.
 
NOTE: Be careful to question the patient to ensure that he/she is actually seeing an improvement in visual acuity.
 
With this in place, measure the range of clear focus for the near point card.
 
  
 If the desired test distance is...	Then	
   
 Approximately midway within the clear focus zone	No further adjustments are necessary.	
 
 At the edge of the clear focus zone closest to the patient	Add -0.25D and measure the range of clear focus again.	
 
 At the edge of the clear focus zone furthest from the patient	Add +0.25D and measure the range of clear focus again.	
  
 
Repeat this step until the near point is approximately midway within the clear zone.
	If the desired test distance is...	Then	Approximately midway within the clear focus zone	No further adjustments are necessary.	At the edge of the clear focus zone closest to the patient	Add -0.25D and measure the range of clear focus again.	At the edge of the clear focus zone furthest from the patient	Add +0.25D and measure the range of clear focus again.
If the desired test distance is...	Then								
Approximately midway within the clear focus zone	No further adjustments are necessary.								
At the edge of the clear focus zone closest to the patient	Add -0.25D and measure the range of clear focus again.								
At the edge of the clear focus zone furthest from the patient	Add +0.25D and measure the range of clear focus again.								

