3.2. Inclusion Criteria

Potential subjects must satisfy all of the following criteria to be enrolled in the study:

Inclusion Criteria after Screening:

1. The subject must read, understand, and sign the STATEMENT OF INFORMED CONSENT and receive a fully executed copy of the form.
2. The subject must appear able and willing to adhere to the instructions set forth in this clinical protocol.
3. The subject must be at least 40 years of age and not greater than 70 years of age at the time of consent.
4. Subjects must own a wearable pair of spectacles if required for their distance vision.
5. The subject must be an adapted soft contact lens wearer in both eyes (i.e. wears lenses a minimum of 2 days per week for at least 6 hours per wear day, for 1 month of more duration).
6. The subject must either already be wearing a presbyopic contact lens correction (e.g., reading spectacles over contact lenses, multifocal or monovision contact lenses, etc.) or if not respond positively to at least one symptom on the “Presbyopic Symptoms Questionnaire” (Appendix E).

Inclusion Criteria after Baseline:

7. The subject's distance spherical equivalent refraction (vertex corrected if ≥ -4.25 D) must be in the range of -1.25 D to -5.75 D or +0.75 D to +3.25 D in each eye.
8. The subject's refractive cylinder must be ≤ 0.75 D in each eye.
9. The subject's ADD power must be in the range of +0.75 D to +2.50 D.
10. The subject must have distance best corrected visual acuity of 20/20⁻³ or better in each eye.

Clinical Study Protocol

Johnson & Johnson Vision Care, Inc.

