1.13	Keratometry	Keratometry will be performed OD and OS and the steep and flat dioptic power and corresponding meridians recorded.
1.14	Subjective Refraction and Distance Visual Acuity	An optimal, binocular balanced distance spherocylindrical refraction will be performed. Record the refraction and distance visual acuity to the nearest letter. Note: Best distance visual acuity with spherocylindrical refraction must be at least 20/20³ in each eye for the subject to be eligible in the study.
1.15	Near ADD Determination	The near reading addition will be determined using the binocular crossed cylinder technique (BCC) at 40 cm followed by optimization in a trial frame in step 1.17 below.
1.16	Ocular Dominance	Determine the distance ocular dominance with the best distance correction in place using a +1.00-blur test. If the results are equivocal use the sighting dominance test to determine the dominant eye used for the study.
1.17	ADD Refinement	Place the BCC result in the trial frame and refine the near prescription with trial lenses (or flippers) under binocular conditions.

Clinical Study Protocol
Johnson & Johnson Vision Care, Inc.

1.18	Near Visual Acuity	Using the ETDRS 2000 Series Chart 1 or 2 near card placed at 40 cm. Record the near visual acuity OD, OS and OU at 40 cm.	
1.19	Biomicroscopy	
FDA Slit Lamp Classification Scale* will be used to grade the findings and determine eligibility.
 
*note: for corneal staining note location (nasal, temporal, superior, inferior or central)
 
If any of these slit lamp findings are Grade 2 or higher, the subject will be discontinued. If discontinued a final examination must be completed.
 
If the clearance of the fluorescein needs to be expedited, preservative-free rewetting drops may be instilled.
	
1.20	Eligibility after Baseline	
All responses to Inclusion Criteria questions must be answered "yes" and all responses to Exclusion Criteria questions must be answered "no" for the subject to be considered eligible.
 
If so, proceed to lens fitting. If not, complete the final evaluation and discharge the subject.
	

Visit 1: Treatment 1 Lens Fitting		
Step	Procedure	Details
1.21	Lens Selection	The lens powers (distance and ADD) will be selected based upon the calculation provided in EDC. Record the test lens parameters (power and lot number).

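### Near-ADD work instruction: the edge rows in steps 6 and 7 move 40 cm away from the midway end point that the same steps set

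*Protocol*

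**What the plan says.** Protocol 7.2, step 1.15: "The near reading addition will be determined using the binocular crossed cylinder technique (BCC) at 40 cm". Step 1.17 then says: "Place the BCC result in the trial frame and refine the near prescription with trial lenses (or flippers) under binocular conditions".

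The procedure is in Appendix H, Determination of Near Addition. Step 6 handles a tentative ADD that is too strong and step 7 one that is too weak. Each ends with a three-row table, used after the zone of clear focus has been measured:

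- Test distance about midway in the zone: no further change.
- Test distance "Near the edge of the clear focus zone closest to the patient" (step 6; step 7 has an equivalent row): "Add -0.25D and measure the range of clear focus again".
- Test distance near the furthest edge (in step 7, "At the edge of the clear focus zone furthest from the patient"): the same instruction with +0.25 D.

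Step 6 closes with "Repeat this step until the near point is approximately midway in the clear zone", and step 7 closes to the same effect.

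The resulting ADD is used in three places:

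- Inclusion criterion 9: "The subject's ADD power must be in the range of +0.75 D to +2.50 D".
- Step 1.21, where an EDC calculation selects the distance and ADD lens powers.
- The CLUE, visual acuity and secondary models (Protocol 14.5 and 14.6; SAP 11.1 and 11.2), where ADD power is a covariate.

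**The concern.** The tables are a feedback rule: measure where the test distance sits in the clear zone, change the power, measure again, and stop at midway. Such a rule works only if each correction reduces the error. Here the sign in both edge rows appears to increase it.

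The procedure also tends to lead into one of those rows. Step 6 takes plus away until clarity begins to fall, which leaves 40 cm at the edge nearest the patient. The table then calls for more minus.

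At stake is the consistency of a baseline measurement that gates entry and lens selection. The work instruction's grading scale records ADD in 0.25 D units, so one adjustment equals one recording unit. The training requirement is read-only, so the text itself is the control on how sites perform the measurement.

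**Working it through.** **Inputs from the documents.** The test distance is 40 cm, a vergence of 100/40 = 2.50 D. The step is 0.25 D. The sign convention is fixed by step 6 ("If the tentative ADD is too strong (too much plus"): plus strengthens the ADD and minus weakens it.

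**Assumption.** The dioptric width of the clear zone, a, is not given. I used 0.50, 0.75, 1.00 and 1.50 D. The direction of the result does not depend on it.

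**Model.** For ADD A, thin-lens vergence puts the near edge at 100/(A + a) cm and the far edge at 100/A cm. Raising A brings both edges closer to the patient; lowering A moves both away. The offset of 40 cm from the dioptric centre of the zone is d = 2.50 - (A + a/2). A positive d means that 40 cm lies on the patient's side of centre.

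**Direction, for any width.**

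- Near edge: A + a = 2.50, so d = +a/2. The printed -0.25 D makes d = a/2 + 0.25.
- Far edge: A = 2.50, so d = -a/2. The printed +0.25 D makes d = -(a/2 + 0.25).

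Either way the offset grows by 0.25 D.

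**One printed step, starting with 40 cm exactly at an edge.**

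| Width a (D) | Edge | ADD | Zone before (cm) | ADD after | Zone after (cm) | Offset (D) |
|---|---|---|---|---|---|---|
| 0.50 | near | 2.00 | 40.0-50.0 | 1.75 | 44.4-57.1 | 0.25 to 0.50 |
| 0.50 | far | 2.50 | 33.3-40.0 | 2.75 | 30.8-36.4 | 0.25 to 0.50 |
| 0.75 | near | 1.75 | 40.0-57.1 | 1.50 | 44.4-66.7 | 0.375 to 0.625 |
| 0.75 | far | 2.50 | 30.8-40.0 | 2.75 | 28.6-36.4 | 0.375 to 0.625 |
| 1.00 | near | 1.50 | 40.0-66.7 | 1.25 | 44.4-80.0 | 0.50 to 0.75 |
| 1.00 | far | 2.50 | 28.6-40.0 | 2.75 | 26.7-36.4 | 0.50 to 0.75 |
| 1.50 | near | 1.00 | 40.0-100.0 | 0.75 | 44.4-133.3 | 0.75 to 1.00 |
| 1.50 | far | 2.50 | 25.0-40.0 | 2.75 | 23.5-36.4 | 0.75 to 1.00 |

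In all eight rows 40 cm is outside the zone after one step. If 40 cm starts 0.25 D or more inside the edge, one step moves it towards or onto that edge but not past it. A step of the opposite sign reduces the offset by 0.25 D in every row; I computed that only to confirm that the direction, not the step size, is at fault.

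**Midway read in centimetres.** The direction is the same. For a = 1.00 at the near edge, the zone's midpoint moves from (40.0 + 66.7)/2 = 53.3 cm to (44.4 + 80.0)/2 = 62.2 cm, further from 40 cm.

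**Repetition.** Repeating the edge row gives 1.50, 1.25, 1.00, 0.75 and so on, or 2.50, 2.75, 3.00 and so on, and never reaches midway. Redoing the whole step instead of only the table does not rescue it. Step 6's clarity test stops at the proximal edge, not at the centre. Step 7's clarity test can restore the plus that the table removed, after which the same row removes it again.

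**The case against.** The case on the other side accepts the sign conflict and attacks its consequences. Much of that stands.

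- **A reader might infer that the rule yields a specific wrong ADD.** It does not. Midway is the only stopping point and the zone is re-measured after each step, so the literal rule fails to finish. Once 40 cm is outside the zone, no row strictly applies. An experienced examiner may notice and override the text.
- **A reader might infer a 0.75 D error, LOW instead of HIGH.** This compares +1.25 with a centred +2.00 at an assumed 1.0 D width. At +1.25, 40 cm is already outside the zone, so the instruction would not accept that value as final. The bands come from the approved-product insert in Appendix C, not from a visible rule for the test lens.
- **A reader might infer that the tables also contradict the too-strong heading of step 6.** That heading describes the ADD on entry. Minus is added before the table is used, so the zone has already moved outwards.
- **A reader might infer doubt about which of FAL100, FAL101 and FAL102 was validated.** Step 1.21 records the lens power and lot worn, and no hypothesis is specific to one ADD design.

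Two further points are fair. Steps 1.28 and 2.9 allow modifications, and dispensing requires acceptable vision and at least 20/30 distance acuity with both eyes, so the starting ADD does not fix the lens worn. Also, in a single-arm study against fixed thresholds, a poor ADD would be expected to worsen the results; no route to a false pass is shown.

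None of this resolves the conflict between the edge rows and the end point. Later modifications also do not change the ADD used for eligibility.

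**Conclusion.** The point holds in a limited form. In steps 6 and 7 both edge rows work against the end point of their own step, by 0.25 D per adjustment and for any zone width. Once an edge row applies, the procedure as written cannot end at midway, so the recorded ADD depends on when the examiner stops or departs from the text.

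Confidence is high on the contradiction and low on its impact. A subject already at midway is unaffected, and the number of others cannot be estimated. The EDC formula and the content of Appendix G are not visible, so the path from a 0.25 D difference to a different lens cannot be traced. The point assumes that sites use this work instruction for steps 1.15 and 1.17. Step 1.17 itself does not mention centring the zone, and the instruction's opening steps are redacted, although steps 6 and 7 fix the sign convention themselves. Sample size, power and type I error are unaffected.

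**What to change.** Reconcile the two edge rows in step 6, and the matching rows in step 7, with the midway end point stated in those steps. Reissue the work instruction with a short training note before further ADDs are refined.

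The grading scale provides for the distance tested and the range of clear focus in centimetres. Where these were recorded for subjects already refracted, check whether 40 cm lies about midway in the range, and list those for whom it does not.

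The cost is a correction to one document, a training note and a data check. No visit, procedure or sample size changes.

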5. GRADING SCALE

- ADD Power: Diopters (0.25D increments)
- Distance tested and range of clear focus: cm (one unit increments)
- Visual Acuity: Snellen

7. TRAINING REQUIREMENTS

The training requirement for this document is "Read Only."

**Clinical Study Protocol
Johnson & Johnson Vision Care, Inc.**

CTP-2006, NEAR LOGMAR VISUAL ACUITY MEASUREMENT PROCEDURE

1. OVERVIEW

This document contains the procedure to measure near visual acuity using logMAR visual acuity charts.

2. MATERIALS

- Near visual acuity charts (as specified in the protocol), for example:
 - Guillon-Poling Charts (**NOTE: Guillon-Poling charts are recorded in -10 logMAR**)
 - Precision Vision Sloan ETDRS or landolt C logMAR visual acuity charts
 - Or other equivalent near logMAR visual acuity chart
- Goggles with Neutral Density (ND) filters with 20%-32% transmittance, as specified in the protocol
- Near chart stand or near light box
- Light meters for measuring chart luminance and room illumination

3. SETUP

The following steps are used in the setup of the examination room and equipment prior to evaluation of the subject.

Step	Action
1	
Insert visual acuity chart on the illuminator cabinet, chart stand or have subject hold the test card depending on test used and protocol instructions.
 
NOTE: for tests conducted under low luminance conditions, have the subject wear the goggle labeled as "Near" or "N"

2	
Verify room illumination and chart luminance per protocol requirements with a light meter (reference "Verification of logMAR chart luminance and room illumination" CTP-2059). The suggested chart luminance (unless otherwise specified in the clinical study protocol) is:
 
 • High luminance: 225 - 275 cd/m² (≈10.8-11.1 EV) • Low luminance: 45 – 55 cd/m² (≈8.5-8.8 EV)

4. ETDRS VA MEASUREMENT

The following steps are used in the measurement of monocular and/or binocular (as specified in the clinical study protocol) near logMAR visual acuity (VA).

Step	Action					
1						
2	
Instruct the subject to start with the largest line he/she can easily read the whole line.
 
 
 If the subject...	Then	
 
 Misses any letter in the first attempted line	Ask the subject to re-start with a line above the line just read until the subject correctly reads all 5 letters of the line or the subject reaches the top line of the chart.	
 
		If the subject...	Then	Misses any letter in the first attempted line	Ask the subject to re-start with a line above the line just read until the subject correctly reads all 5 letters of the line or the subject reaches the top line of the chart.
If the subject...	Then					
Misses any letter in the first attempted line	Ask the subject to re-start with a line above the line just read until the subject correctly reads all 5 letters of the line or the subject reaches the top line of the chart.					

	Is unable to read at least 3 letters on the top line of the chart	Move the subject closer, to 33cm, or further away, to 50cm, from the chart (depending on what improves their vision) and repeat the step 2, unless the study protocol states that this is not allowed. Record the new test distance in the CRF and proceed to the next step.
	Can't correctly read 3 or more letters after moving the chart to 33 and/or 50 cm test distance, or if moving the chart was not allowed in the protocol	Record the number of letters missed in the top line proceed to step 6. If using EDC, you will need to answer an automated query.
3		
It is required that responses are recorded starting from a line where no letters are missed. For lines where no letters are missed, check the “None” box in EDC next to that line of letters (or record “0” missing next to the line if recording on paper). After the subject passes the first attempted line, instruct the subject to continue reading lines down through the chart. For each line read, line through letters that are missed by the subject and record the number of letters missed next to each line. For each subsequent line read, check the box next to each letter missed by the subject, or check the “None” box if no letters are missed. NOTE: If recording on paper, place a line through each letter missed, or mark a line through the entire row of letters if they are all missed, and then record the number of letters missed (0 to 5) next to each line.

4		
Encourage the subject to try to continue to read each line. If the subject says he/she cannot see the next line, encourage him/her to take his/her best guess.

5		
Stop the test only when the subject misses three or more letters on a single line. (NOTE: If the subject misses three letters on a line, and there are still letters that they haven't attempted to read have the subject attempt to read the remaining letters and record the results.) Otherwise, continue to encourage the subjects to keep reading the next line below till reaching the bottom line. If subjects correctly read all 5 letters on the last line, stop the test and record 0 missing without moving subjects further away from the chart.

6		
Repeat procedure with the same eye or complete the other eye the appropriate number of times, per protocol requirement.

6. DATA MANAGEMENT

The electronic data capture system will automatically convert logMAR visual acuity if the chart is used at a distance other than what it was designed for. The formula to compute logMAR score at a different distance other than the chart specified distance is: $\text{LogMAR2} = \text{LogMAR1} + \log_{10}(D1/D2)$,

